7.4.2 Analysis of Secondary Variables

The key secondary efficacy variable will be the change from baseline to end of treatment in mean volume voided per micturition. The other secondary variables are:

- Change from baseline to end of treatment in symptom bother and total health related quality of life scores as assessed by OAB-q questionnaire, and

- Change from baseline to end of treatment in Patient Perception of Bladder Condition (PPBC).

Change from baseline to end of treatment in mean volume voided

Change from baseline to end of treatment in mean volume voided will be tested using a stratified Analysis of Covariance (ANCOVA) model. The response variable will be the mean change in mean volume voided from baseline to the end of the study with treatment group and gender as fixed factors and baseline mean volume voided as the covariate in the model. Age group ($<75, \geq 75$) will be included as the stratification factor. As part of the ANCOVA results, LS means and two-sided 95% CIs for mean changes from baseline within each treatment group will be provided. Differences in LS means between mirabegron and placebo will be derived together with 95% CIs and p-values.

Sensitivity analysis

As a sensitivity analysis, a non-parametric test will be applied in investigating MVV. Differences in change from baseline to end of treatment in mean volume voided per micturition between mirabegron and placebo will be analyzed using a stratified rank ANCOVA model. The response variable will be the standardized ranks of the change from baseline to end of treatment in mean volume voided per micturition. Treatment group and gender will be fixed factors in the model while the standardized ranks of the baseline mean volume voided per micturition will be included as covariate. Age group ($<75, \geq 75$) will be included as the stratification factor.

Change from baseline in symptom bother and total health related quality of life scores as assessed by OAB-q questionnaire.

Differences in change from baseline of symptom bother and total health related quality of life scores as assessed by OAB-q between mirabegron and placebo will be analyzed using a stratified ANCOVA model. The response variable will be the change from baseline in symptom bother and total health related quality of life scores. Treatment group and gender will be fixed factors in the model while the baseline symptom bother and total health related quality of life scores will be included as covariate. Age group ($<75, \geq 75$) will be included as the stratification factor. As part of the ANCOVA results, LS means and two-sided 95% CIs for mean changes from baseline within each treatment group will be provided.

Change from Baseline in Patient Perception of Bladder Condition (PPBC)

Differences in change from baseline of PPBC between mirabegron and placebo will be analyzed using a stratified ANCOVA model. The response variable will be the change from baseline in PPBC. Treatment group and gender will be fixed factors in the model while the baseline symptom bother and total health related quality of life scores will be included as covariate. Age group ($<75, \geq 75$) will be included as the stratification factor. As part of the ANCOVA results, LS means and two-sided 95% CIs for mean changes from baseline within each treatment group will be provided.

Responder Analysis for OAB-q and PPBC

A responder analysis will be performed for OAB-q at Week 12 or LOCF using a logistic regression model. This will be based on the change in percentage OAB-q from baseline. The definition of the categories of the response variable is based on the results of the OAB-q study by Coyne *et al*, 2007. The responder groups will be defined as follows:

A responder is a subject with a minimally important difference (MID) $\geq 10\%$ change in OAB-q while a non-responder will be a subject with a MID $< 10\%$ change in OAB-q.

Two responder analyses will be performed for PPBC at Week 12 or LOCF using a logistic regression. Two logistic regression models will be fitted with binary response variables that are based on change from baseline in PPBC. The response variables will be categorized as follows;

- Improvement: ≥ 1 point improvement from baseline to post-baseline for PPBC
- Major improvement: ≥ 2 point improvement from baseline to post-baseline for PPBC

Logistic regression for the responder analysis will include treatment group, gender and baseline measurements as the explanatory variables.

7.4.3 Analysis of Other Variables

The analysis of change from baseline scores for the following additional efficacy endpoints will be analyzed in the same way as described for the mean number of micturitions, i.e., using a stratified ANCOVA including treatment (placebo and mirabegron) and genders a fixed factor and baseline as a covariate. Age group will be used as the stratification variable.

- Change from baseline in mean number of urgency episodes (grade 3 and/or 4)/24 hour
- Change from baseline in mean number of urgency incontinence episodes/24 hour
- Change from baseline in mean level of urgency
- Change from baseline in mean number of nocturia episodes/24 hour
- Change from baseline in subscale score from OAB-q scores
- Change from baseline in TS-VAS
- Change from baseline in University of Alabama, Birmingham - Life Space Assessment (UAB-LSA)

Responder analysis as defined by $\geq 50\%$ reduction from baseline in mean number of incontinence episodes/24 hours from baseline or zero incontinence episodes post-baseline.

7.4.4 Exploratory Analysis

7.5 Analysis of Safety

Safety analysis will be performed for adverse events (AEs) and vital signs using the SAF. No inferential comparison between treatment groups will be performed for the safety analysis in

this study with the exception of the change from baseline in Montreal Cognitive Assessment Test (MoCA) and for vital signs analysis.

Differences in change from baseline of MoCA scores between mirabegron and placebo will be analyzed using a stratified ANCOVA model. The response variable will be the change from baseline in MoCA scores. Treatment group and gender will be fixed factors in the model while the baseline symptom bother and total health related quality of life scores will be included as covariate. Age group (<75, \geq 75) will be included as the stratification factor. As part of the ANCOVA results, LS means and two-sided 95% CIs for mean changes from baseline within each treatment group will be provided.

Vital Signs will be summarized by treatment group and by Home Based Blood Pressure Monitoring (HBPM) versus office based using descriptive statistics for baseline value, specified post-baseline time point values (Week 4, Week 8, Week 12/EOT), and change from baseline to each specified post-baseline time points. Office based and morning and evening blood pressure will be reported separately. For HBPM the first reading from each time period will be discarded and the subsequent two readings for each time period will be averaged over the 3-day diary. HBPM and office based monitoring will be reported separately (See [Appendix 4](#)).

7.5.1 Adverse Events

Adverse events will be coded using the Medical Dictionary for Regulatory Activities (MedDRA). The number and percentage of AEs, SAEs, AEs leading to discontinuation, and AEs related to study drug will be summarized by system organ class, preferred term and treatment group. The number and percentage of AEs by severity will also be summarized. All AEs will be listed.

The number and percentage of TEAEs, serious TEAEs, and discontinuations due to a TEAE will be summarized by System Organ Class, Preferred Term, and treatment group. In addition, TEAEs will be summarized by relationship to study drug as determined by the Investigator and by severity for each treatment group.

7.5.2 Laboratory Assessments

Laboratory variables (biochemistry, hematology, and urinalysis) will be descriptively summarized for Screening and Week 12/End of Treatment and change from Screening to End of Treatment will be summarized by treatment group.

For each hematology and biochemistry laboratory parameter, laboratory test results will be classified as low (L), normal (N), or high (H) according to the laboratory-supplied reference ranges. Shift tables of reference range changes from Screening to Week 12/End of Treatment and most extreme value during the double-blind treatment period by treatment group will be summarized.

Laboratory abnormalities will be evaluated based on the Potential Clinically Significant (PCS) laboratory criteria. For each laboratory PCS criterion, the number and percent of subjects who have a laboratory value meeting the PCS criteria during the double-blind

treatment period will be summarized by treatment group. The directions of changes (high or low) in PCS will be indicated in the tables.

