12.2 Appendix 2: Liver Safety Monitoring and Assessment

If laboratory testing for a subject enrolled in study and receiving study drug reveals an increase of serum aminotransferases (AT) to $> 3X$ ULN, or bilirubin $> 2X$ ULN, at least all four of the usual serum hepatic measures (ALT, AST, ALP, and TBL) must be repeated. Testing must be repeated within 48-72 hours of notification of the test results. For studies for which a central laboratory is used, alerts will be generated by the central lab regarding moderate and marked liver abnormality to inform the Investigator, study monitor and study team. Subjects must be asked if they have any symptoms suggestive of hepatobiliary dysfunction.

Definition of Liver Abnormalities

Confirmed abnormalities will be characterized as moderate and marked where ULN:

	ALT or AST		Total Bilirubin
Moderate	$> 3 \times \text{ULN}$	or	$> 2 \times \text{ULN}$
Marked (Hy's Law)	$> 3 \times \text{ULN}$	and	$> 2 \times \text{ULN}$

In addition, the subject must be considered to have marked hepatic abnormalities for any of the following:

- ALT or AST $> 8X$ ULN
- ALT or AST $> 5X$ ULN for more than 2 weeks
- ALT or AST $> 3X$ ULN and INR > 1.5
- ALT or AST $> 3X$ ULN with the appearance of fatigue, nausea, vomiting, right upper quadrant pain or tenderness, fever, rash and/or eosinophilia ($> 5\%$).

The Investigator will determine if abnormal liver function results, other than as described above, qualify as moderate or marked abnormalities and require additional monitoring and follow-up.

Follow-up Procedures

Confirmed moderate and marked abnormalities in hepatic functions must be thoroughly characterized by obtaining appropriate expert consultations, detailed pertinent history, physical examination and laboratory tests. The site must complete the Liver Abnormality Case Report Form (LA-CRF) or an appropriate document. Subjects with confirmed abnormal liver function testing must be followed as described below.

Confirmed moderately abnormal LFTs must be repeated 2-3 times weekly then weekly or less if abnormalities stabilize or the study drug has been discontinued and the subject is asymptomatic.

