7.1.1 Last Observation Carried Forward (LOCF)

For the efficacy diary data the EoT value will be calculated as the average or the count of the valid diary measurements reported in the last 3 valid diary days of the analysis visit window prior to EoT. For subjects who withdraw before week 12, the last available post-baseline average of the diary data measurements will be carried forward as the EoT value (LOCF).

For the non-diary efficacy data and safety data, the EoT value will be the last measurement within the week 12 visit day windows. For subjects who withdraw before week 12 the last measurement within the analysis visit window of the last available post-baseline visit will be carried forward as the EoT value (LOCF).

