7.5.2 Clinical Laboratory Evaluation

Laboratory variables (biochemistry, hematology, and urinalysis) will be descriptively summarized for Screening and Week 12/End of Treatment and change from Screening to End of Treatment will be summarized by treatment group.

Quantitative clinical laboratory variables, i.e. hematology, biochemistry, and urinalysis will be summarized using mean, standard deviation, minimum, maximum, Q1, Q3, and median for each treatment group at each visit. Additionally, a within-subject change will be calculated as the post-baseline measurement minus the baseline measurement and summarized in the same way.

Laboratory results will be classified as low (L), normal (N), or high (H) at each visit according to the laboratory supplied reference ranges. Shift tables of reference range changes from Screening to Week 12/End of Treatment during the double-blind treatment period by treatment group will be summarized for all laboratory values.

Laboratory abnormalities will be evaluated based on the Potentially Clinically Significant (PCS) laboratory criteria. For each laboratory PCS criterion, the number and percent of subjects who have a laboratory value meeting the PCS criteria during the double-blind treatment period will be summarized by treatment group. The directions of changes (high or low) in PCS will be indicated in the tables. The pre-defined criteria for PCS laboratory values are presented below.

Potentially Clinically Significant Laboratory Criteria			
Laboratory Parameter	Unit	Low PCS Criterion	High PCS Criterion
Hematology			
Hemoglobin	g/L	< 80	>180
Hematocrit	Fraction	< 0.25	> 0.55
Erythrocyte (Red Blood Cell Count)	$\times 10^{12}/L$	< 2.5	> 7.0
Platelet Count	$\times 10^9/L$	< 120	> 500
Leukocyte (White Blood Cell Count)	$\times 10^9/L$	< 2.5	> 18
Potassium	Meq/L	< 3.0	> 6.0

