7.10.3 Visit Windows

Subjects do not always adhere strictly to the visit timing in the protocol. Therefore, the designation of visits during the double-blind treatment period will be based on the day of

evaluation relative to the start of the double-blind treatment period (day of first dose of double-blind treatment in double-blind treatment period = Day 1 of double-blind treatment period) rather than the nominal visit recorded in the CRF.

To assign a measurement to a study visit during the double-blind treatment period, the first step consists of selecting all measurements falling within the double-blind treatment period as defined above. To further determine the study visit measurement, mutually exclusive relative day windows are used.

If a subject has more than one visit with a measurement included within a window, the assessment closest to the scheduled day will be used. In case of ties between observations located on different sides of the scheduled day, the later assessment will be used. In case of ties located on the same side of the scheduled day (i.e., more than one value for the same day), the mean of the values will be used for continuous variables and the worst value for categorical variables.

It should be noted that if more than one measurement for a parameter is recorded within the same visit window, the above conventions may not lead to the most conservative approach for the by-visit summaries of categorical or numerical variables. The worst individual categorical or numerical value within a visit window may not be identified as the value representative for the analysis visit due to the rules above. However, the worst individual categorical or numerical value will be accounted for in tables summarizing the worst individual categorical or numerical value reported during the double-blind treatment period. All individual values will be provided in a listing.

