7.10.3.1 Analysis Visit Windows for Efficacy and Safety Variables

All the efficacy and safety assessments for a treatment period will be allocated based on the tables below.

Efficacy:

Analysis visit	Target day	Actual assessment day
Screening	Day -28	-38 to -18
Placebo Run-In	Day -14	-17 to 0
Baseline	Day 1	Day 1 ^a
Week 4	Day 30	15-42
Week 8	Day 60	43-70
Week 12/End of Treatment	Day 90	71-98
Follow Up Phone Call	Day 120	EOT+14

After Placebo Run-In, visit windows/study days will be calculated based on the Baseline (Visit 3) date.

Safety:

Analysis visit	Target day	Actual assessment day
Screening	Day -28	-38 to -18
Placebo Run-In	Day -14	-17 to 0
Baseline	Day 1	Day 1 ^a
Week 4	Day 30	2-45
Week 8	Day 60	46-75
Week 12/End of Treatment	Day 90	76-97
Follow Up Phone Call	Day 120	EOT+14

1. After Placebo Run-In, visit windows/study days will be calculated based on the Baseline (Visit 3) date.

For efficacy variables recorded in the 3-day micturition diary, the following rules will apply:

1. As micturition diary data are to be recorded from midnight 3 days prior to a visit to midnight 1 day prior to a visit, micturition diary records which have the same date as a visit date should be excluded from the analysis. Non-micturition questionnaire assessment dates will be compared to the eDiary dates and used to flag which diary records should be excluded.
2. Any diary days which are > 7 days after the last dose of double-blind treatment will not be included in the analysis.
3. Average values or number of episodes for count data will only be calculated if at least 2 valid diary days are available within the specified window. In the case that only 1 valid diary day is available, then no value will be calculated.
4. If there are more than 3 valid diary days available for a visit, the average will be based on the last 3 days prior to the scheduled visit.
5. Duplicate records (same time and episode characteristics) per day during the 3-day micturition diary period will be excluded.

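### SAP 7.5.2 omits the protocol's most-extreme-value laboratory shift table, and two conflicting Week 12 rules can each let a liver repeat stand in for the scheduled Visit 6 result

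*Protocol*

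**What the plan says.** - **Shift tables.** Protocol 7.5.2 plans two for each hematology and biochemistry parameter, from "Screening to Week 12/End of Treatment and most extreme value during the double-blind treatment period by treatment group will be summarized". The matching sentence in SAP 7.5.2 reads "Shift tables of reference range changes from Screening to Week 12/End of Treatment during the double-blind treatment period by treatment group will be summarized". The most-extreme-value part is gone, and the phrase about the double-blind period now attaches to the EoT shift.
- **EoT value.** SAP 7.1.1: "For the non-diary efficacy data and safety data, the EoT value will be the last measurement within the week 12 visit day windows". When a subject withdraws early, the final measurement in the window of that subject's last available visit is carried forward.
- **Several values in one window.** SAP 7.10.3 has a different rule: "the assessment closest to the scheduled day will be used", with ties across the target day going to the later value. It first restricts to measurements in the double-blind treatment period. It gives that period a start (first dose) but no end for laboratory data.
- **Window.** SAP 7.10.3.1, safety table: "Week 12/End of Treatment Day 90 76-97".
- **Sampling.** Protocol Table 3 schedules blood only at Screening and Visit 6.
- **Repeats.** Under protocol Appendix 2, aminotransferases above 3x ULN or bilirubin above 2x ULN require ALT, AST, ALP and total bilirubin to be measured again: "Testing must be repeated within 48-72 hours of notification of the test results". Confirmed moderate abnormalities are then followed 2 to 3 times weekly.

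**The concern.** The protocol promised a table that does not depend on which value is chosen to represent a visit, and the SAP dropped it without comment. In SAP 7.5.3, by contrast, the SAP does comment on a difference from the protocol's description of the vital-signs model. The revision history gives only Protocol Amendment 2 and sponsor comments as reasons for change.

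The omission matters because SAP 7.10.3 itself concedes that its window rules may not pick the most conservative value, and relies on this: "the worst individual categorical or numerical value will be accounted for in tables summarizing the worst individual categorical or numerical value". With Visit 6 as the only scheduled on-treatment sample, a value drawn a few days later under Appendix 2 can become the EoT value. The L/N/H shift and the mean change from Screening would then show a follow-up value in the few subjects with a flagged liver test. Because the two selection rules differ, two programmers could also produce different EoT tables from the same data.

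**Working it through.** The plan states no figure to reproduce here, so the check is a comparison of texts and a count of days.

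**Inputs.** Visit 6 falls on Day 84 +/- 7 in the protocol schedule (Days 77 to 91) and on Day 90 +/- 7 in the SAP schedule (Days 83 to 97). The SAP safety window is Days 76 to 97 with target Day 90. The repeat comes 2 or 3 days after notification. The lag from blood draw to notification is not in the documents; I assume 0 to 3 days and show 5 and 7 as well.

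**Formulas.** With V = Visit 6 day, repeat day R = V + lag + 2 or + 3.
- Final-value rule (SAP 7.1.1): the repeat replaces Visit 6 if R <= 97.
- Nearest-day rule (SAP 7.10.3): the repeat replaces Visit 6 if R <= 97 and |R - 90| <= |V - 90|.

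Each calendar has 15 visit days x 2 repeat days = 30 combinations. Number in which the first repeat replaces Visit 6:

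| Lag (days) | Protocol days, final | Protocol days, nearest | SAP days, final | SAP days, nearest |
|---|---|---|---|---|
| 0 | 30 | 25 | 25 | 13 |
| 1 | 30 | 24 | 23 | 12 |
| 2 | 30 | 23 | 21 | 11 |
| 3 | 30 | 22 | 19 | 10 |
| 5 | 27 | 20 | 15 | 8 |
| 7 | 23 | 18 | 11 | 6 |

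These are calendar combinations, not expected patients.

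**Two examples at a lag of 1 day.**
- V = 84: R = 84 + 1 + 2 = 87 or 84 + 1 + 3 = 88. Both are inside the window and nearer to Day 90 (3 or 2 days away, against 6), so the repeat is chosen under both rules.
- V = 91: R = 94 or 95. The final-value rule takes the repeat. The nearest-day rule keeps Visit 6 (1 day from target, against 4 or 5). The same data give two different EoT values.

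**What other tables still catch.** SAP 7.5.2.1 uses each subject's highest value and counts ALT or AST above 3x ULN, bilirubin above 2x ULN and the two combined. The first two are the Appendix 2 triggers, so a result that forces a repeat also meets a highest-value criterion. ALP is counted above 1.5x ULN.

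**Other analytes.** Of the 14 chemistry tests in Protocol Table 3, five have a highest-value or potentially-clinically-significant (PCS) criterion in the SAP as shown: potassium, ALT, AST, ALP and bilirubin. The other nine (14 - 5) have none: sodium, calcium, chloride, glucose, creatinine, GGT, total protein, albumin and INR. Appendix 2 requires no repeat of these nine. With one scheduled on-treatment sample, their most extreme value is the Visit 6 value unless an optional extra sample is drawn.

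**The case against.** The strongest reply is that nothing important disappears. A reader might infer that the abnormal liver result is overwritten and lost from the analysis. The documents do not support that: SAP 7.5.2.1 reports it by arm from the highest value at the triggering thresholds, and SAP 7.10.3 lists every individual value. This part of the reply stands.

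A reader might also infer that replacement happens in every subject flagged at Visit 6. That does not hold either. It depends on the notification lag, on which visit calendar applies and on which rule is used. The SAP's first step may also exclude a repeat altogether, if the double-blind period is taken to end at the last dose. Nor do the documents say how unscheduled repeats enter the visit-based data; Appendix 2 sends results of additional testing to the liver abnormality form or another document.

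Finally, it is tempting to list GGT, creatinine and glucose as harmed. No mandated repeat would displace them, so for most subjects the missing table would match the one kept.

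The reply does not remove the unexplained omission, the conflict between SAP 7.1.1 and 7.10.3, or the missing end of the period. Nor do threshold counts replace an L/N/H shift: in a subject retested for bilirubin alone, an ALT between 1x and 3x ULN can be replaced and meets no highest-value criterion.

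**Conclusion.** The point holds as a reconciliation between protocol and SAP with a limited effect on safety tables. A planned table is missing without explanation, and the SAP has two rules for the Week 12 value. Under either, a mandated liver repeat can become the EoT value for ALT, AST, ALP and bilirubin in the shift and change-from-Screening tables.

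For lags of 0 to 3 days, this occurs in 30 of 30 combinations (final-value rule) or 22 to 25 (nearest-day rule) on the protocol's visit days, and in 19 to 25 or 10 to 13 on the SAP's. These counts assume that the lag is in that range, that repeats enter the analysis data, and that the double-blind period does not exclude them. The documents settle none of the three.

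Only subjects with a triggering liver result at Visit 6 or at early termination are exposed through mandated repeats, so I expect few; the documents give no expected number. Their abnormality remains visible in the liver table and the listing. Other analytes are exposed only through optional unscheduled samples.

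**What to change.** - **SAP 7.5.2:** restore the protocol's shift table from Screening to the most extreme value in the double-blind period, for every hematology and chemistry parameter.
- **SAP 7.1.1 and 7.10.3:** replace the two rules with one for laboratory data, under which the scheduled Visit 6 or early-termination sample is the EoT value and unscheduled repeats do not replace it.
- **Period:** state when the double-blind period ends for laboratory data, and whether the investigational period in SAP 7.5.2.1 is the same. Let unscheduled values within it enter only the most-extreme-value, PCS and liver tables.
- **Calendars:** reconcile the Day 84 and Day 90 schedules for Visit 6. I do not say which is right, and the sample-based EoT rule works with either.

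The cost is SAP wording and one additional table program. No new data are needed.
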